26. APR 2016

Date

Date

27 17 pr. 1 2016 Date

28 April 2016 Date

STUDY SYNOPSIS

Protocol 1VIT15042

Title: Randomized, placebo-controlled trial of ferric carboxymaltose in Restless Legs Syndrome patients with iron-deficiency anemia

Investigational Drug: Injectafer® (Ferric Carboxymaltose - FCM)

Treatment Phase I and II Primary Objective: To evaluate the efficacy and safety of FCM (750 mg dose x 2) for treatment of Restless Legs Syndrome (RLS) in patients with irondeficiency anemia (IDA).

Long-Term Extension Phase III Primary Objective: To evaluate the duration of effect of prior FCM treatment and to determine the effectiveness of further iron repletion with FCM when RLS symptoms worsen or reoccur.

Study Design: This will be a Phase II, randomized, placebo-controlled study. All subjects who meet the inclusion criteria, with no exclusion criteria, will qualify to enter the Screening Phase. The study will enroll 70 eligible subjects to receive blinded study drug in Treatment Phase I. All eligible subjects will be randomized in a 1:1 ratio to receive a blinded dose of either FCM 750 mg undiluted slow intravenous (IV) push at 100 mg/minute or a Placebo (15 ml of Normal Saline [NS]) IV push at 2 ml/minute on Day 0 and 7.

A subject will be defined at Day 42 as a **Responder** if the International Restless Legs Syndrome Severity Scale (IRLSS) score is ≤ 10 or if the IRLSS score is >10 with a Clinical Global Impression-Improvement (CGI-I) score of much or very much improvement and the subject does not request further treatment for RLS. A subject will be defined as a treatment **Non-Responder** if neither of these criteria are met.

Non-Responders who do not meet the laboratory criteria for additional dosing will be discontinued from the study and treated for RLS as deemed appropriate by the referring physician. Subjects who are Non-Responders at the end of Treatment Phase I and met the necessary laboratory criteria (ferritin <300 ng/mL and a TSAT <45%) will consented for enrollment in Treatment Phase II of the study. These subjects will receive the first of two unblinded doses of FCM (undiluted slow IV push 750 mg 100 mg/minute) on Day 0 of Phase II, which will occur within 7 days of the completing Treatment Phase I visit. The subjects will then receive the second dose of FCM (undiluted slow IV push 750 mg 100 mg/minute) on Day 7. All treated subjects will have blood samples taken for hematology, chemistries and iron indices on Day 14. Treatment efficacy (IRLSS score), medication review and adverse events assessment by phone will be done on Day 28. All subjects will return to the clinic on Day 42 for end of study assessments. Subjects completing Treatment Phase II will be re-evaluated on Day 42 and defined as either a Responder or Non-Responder, using the same criteria described above. Subjects deemed as treatment Non-Responders will be discontinued from the study after final assessments are complete.

Subjects who are evaluated on Day 42 (Week 6) as **Responders** from either Treatment Phase I or Treatment Phase II will continue through into the 46-Week, Long-Term Extension Phase III of the study, and be monitored and assessed by phone for RLS symptoms (IRLSS and Hopkins RLS-Sleep Quality Questionnaire [HRSQ]) and adverse events on (approximately every 9 weeks) Weeks 15, 25, 34, 43 and 52 (final follow-up visit). During Phase III subjects may receive additional unblinded treatments with FCM if at any time the subject reports worsening of RLS symptoms (an increase >4 points on the IRLSS compared to the last evaluation captured for that subject) and laboratory criteria are met (ferritin <300 ng/mL and a TSAT <45%). Subjects will receive a single FCM 750 mg undiluted slow IV push at 100 mg/minute. See section 6.6 for dosing and assessment outline. No additional treatment will be allowed after the Week 46. A final face-to-face study visit will occur on Week 52 (approximately 365 days since initial Day 0 Treatment). If a clinic visit is not possible, final evaluation will be completed by phone.

All subject assessments (screening through end of study) are in the schedule of events (section 3.2.1).

Study Drug Dosing Regimen:

Treatment Phase I: Subjects will be randomized to receive either a 750 mg undiluted slow IV push (100 mg/minute) of FCM or Placebo (15 ml of Normal Saline [NS]) IV push at 2 ml/minute on Day 0 and 7.

Treatment Phase II: Non-Responders from Phase I who qualify will receive an unblinded 750 mg undiluted slow IV push (100 mg/minute) of FCM on Day 0 and 7 of Phase II.

Long-Term Extension Phase III: Qualified subjects can potentially receive an unblinded single 750 mg undiluted slow IV push (100 mg/minute) of FCM when RLS symptoms worsen or reoccur.

Efficacy and Safety Follow-up:

Primary efficacy endpoint in **Treatment Phase I** is to determine the effectiveness of FCM in improving RLS severity associated with IDA. Effectiveness will be evaluated by:

- IRLSS score change from baseline to Day 42 with comparison between FCM vs. Placebo.
- CGI-I at Day 42.

Primary efficacy endpoint in **Treatment Phase II** is to determine the effectiveness of an additional unblinded single FCM treatment in improving RLS severity in non-responders from Treatment Phase I. Effectiveness will be evaluated by:

- IRLSS score change from baseline (For Phase II the "baseline" is established on Day 42 of Phase I) compared to Day 42 of Treatment Phase II
- - CGI-I at Day 42 in Treatment Phase II.

Secondary efficacy endpoints evaluated in both Treatment Phase's I and II are:

- Number of treatment responders at Day 42 (Treatment Phase I).
- Number of treatment responders at Day 42 (Treatment Phase II).
- IRLSS score change from Baseline (For Phase II the "Baseline" is established on Day 42 of Phase I) compared to Day 42 of Treatment Phase II.
- Number of Responders at Day 42 who receive FCM vs. Placebo in Treatment Phase I.
- Number of Responders at Day 42 in Treatment Phase II who receive FCM vs. Placebo in Treatment Phase I.
- CGI-I and PGI-I at each visit and percentage of subjects who are much or very much improved at Day 42. (Treatment Phase I and II).
- Change in IRLSS score from Day 42 (Treatment Phase I and II).
- Change from baseline brain MRI-determined iron concentration in the substantia nigra at or within 4 days after Day 42 (Treatment Phase I and II).
- Change in sleep quality, Medical Outcome Survey for Sleep (MOS), from Day 42 for Treatment Phase I and II subjects.

Primary efficacy endpoint in **Long-Term Extension Phase III** is to evaluate the duration of effect of FCM as defined as the number of weeks from the initial treatment without need for further treatment. Initial treatment is defined as Day 0 of Phase I for Responders in Phase I and Day 0 of Phase II for Responders in Phase II.

Secondary object is to determine the effectiveness (number of subjects who remain in the study) of additional FCM treatment, in the Long-Term Extension, in those who have worsening of RLS symptoms after the initial response.

Primary safety endpoint is to determine the safety of FCM in RLS patients with IDA

- Safety Evaluations will include:
 - Adverse events
 - Laboratory assessments, including hematology (Hgb, Hct, RBC, WBC, MCV, MCH, MCHC, RDW, platelets, differential count), iron indices (serum iron, serum ferritin, and total iron binding capacity (TIBC), percentage serum transferrin saturation (TSAT)), clinical chemistry (sodium, potassium, chloride, BUN, creatinine, albumin, alkaline phosphatase, total bilirubin, gamma-GGT, AST, ALT, LDH, calcium, phosphorus, glucose, bicarbonate)
 - Vital signs
 - Physical examinations.

Exploratory Aims:

- 1. Evaluate potential predictors of Day 42 (Treatment Phases I and II) treatment response using clinical, hematologic, and brain MRI data.
- 2. The change from baseline in MRI-determined iron concentration for other brain regions.
- 3. Correlation between changes in brain iron distribution and measures of peripheral iron status, RLS severity, and sleep quality.

- 4. Correlation between CBC, iron indices, and change from Baseline to Day 42 (Treatment Phases I and II) RLS severity, sleep, and PGI-I.
- 5. Correlation of baseline Vitamin D and post dose change in phosphate.
- 6. Vitamin D at each visit.

Inclusion Criteria:

- 1. Male or female subject ≥ 18 years of age who is able to give informed consent.
- 2. Confirmed diagnosis of RLS based on the Cambridge-Hopkins Diagnostic Questionnaire (CHDQ) and the Hopkins-Hening Telephone Diagnostic Interview (HDTI).
- 3. IRLSS score \geq 15 plus RLS symptoms for at least 3 months and currently occurring \geq 2 nights per week.
- 4. Iron-deficiency anemia defined as an Hgb <12 g/dl with a ferritin <20 ng/mL, or ferritin <100 when TSAT is <18%.
- 5. Subjects on sleep medication must be on a stable dose for at least 6 months prior screening.
- 6. Subjects at risk for pregnancy must have a negative pregnancy test at screening and be practicing an acceptable form of birth control, have had a hysterectomy or tubal ligation, or otherwise be incapable of pregnancy, or have practiced any of the following methods of contraception for at least one month prior to study entry: hormonal contraceptives, spermicide with barrier, intrauterine device, or partner sterility.

Exclusion Criteria

- 1. Disorders that require treatment with the same medications used for RLS include: peripheral neuropathy and neurodegenerative disorders (i.e. Parkinson's disease or dementia).
- 2. Current (past 4 weeks) use of drugs that may cause or treat RLS, e.g. opioids, calcium channel alpha-2-delta ligands, anti-depressants, dopaminergic agonist or antagonists, or centrally-acting antihistamines.
- 3. Any medical conditions contraindicated to MRI.
- 4. Abnormal MRI at baseline that would confound the outcome measures.
- 5. Secondary RLS due to neurological conditions or head trauma.
- 6. History of hemochromatosis, hemosiderosis, other iron storage disorders or iron metabolism disorders.
- 7. Women with clinically significant uterine bleeding (>200 cc blood loss) during the six months prior to screening.
- 8. Liver transaminases (AST or ALT) greater than two times the upper limit of normal (ULN).
- 9. Known positive Hepatitis B antigen (HBs Ag), unless positive test can be attributed to receipt of Hepatitis B vaccination in childhood or Hepatitis C viral antibody (HCV) with evidence of active hepatitis (i.e., AST/ALT greater than two times the ULN).
- 10. Known positive HIV-1 or HIV-2 antibodies (anti-HIV).
- 11. Active acute or known chronic infections.
- 12. Rheumatoid arthritis with symptoms or signs of active inflammation.

- 13. Pregnant and lactating women.
- 14. Known hypersensitivity reaction to any component of Injectafer® (ferric carboxymaltose).
- 15. Previously randomized to Injectafer® (FCM or VIT-45) in a clinical trial.
- 16. Previous IV iron treatment for RLS.
- 17. Parenteral iron, erythropoiesis stimulating agent use or blood transfusion within six weeks prior to the screening visit.
- 18. Planned elective surgery during the study year.
- 19. Chronic alcohol or drug abuse within the past six months.
- 20. Any other pre-existing laboratory abnormality, medical condition, or disease that, in the opinion of Investigator, may cause the subject to be unsuitable for the study or place the subject at potential risk from being in the study, e.g. a malignancy, uncontrolled hypertension, unstable ischemic heart disease, or uncontrolled diabetes mellitus.
- 21. Subject is unwilling or has conditions that would prohibit them from complying with the study requirements.

RLS Therapy:

Subject should not be receiving treatment for RLS. All treatment for RLS should be discontinued at least 4 weeks prior to screening.

Study Duration – One year:

- Screening Phase: up to 14 days
- Treatment Phase I: 42 days
- Treatment Phase II: 42 days
- Long-term Extension Phase III: up to 46 weeks

Number of Subjects / Sample Size:

Enrollment is planned for completion (reaching Day 42 final assessment) of 70 randomized subjects (35 per treatment group). Based on Study 1VIT05009 in RLS subjects without IDA, approximately 50% of subjects in the FCM group and 15% of subjects in the placebo group are anticipated to have much or very much improvement on the CGI-I.³⁵ The proposed sample size provides >85% power to detect this difference with the chi-square test. The mean treatment difference and standard deviation of 5.0 (7.3) is estimated for change from Baseline to Day 42 for IRLSS score. The proposed sample size provides >80% power to detect this difference with the unpaired t-test.

Statistical Analyses:

The percentage responding to treatment will be evaluated for each drug condition in Treatment Phase I to determine the treatment difference at Day 42. This will be calculated from the IRLSS as change from Baseline and for the CGI-I with response determined as much or very much improved (scores of 1 or 2). All scores greater than 2 on the CGI-I are considered to indicate no significant response. For Phase II, the proportion of treatment non-responders in Phase I who respond to FCM in Phase II will be estimated and the IRLSS score, CGI-I, and PGI-I will be summarized at Day 42. The duration of treatment over the follow-up to end of study will be described as the percentage of responders and the IRLSS score change from Baseline at each time point. Time to first FCM dose after start of Phase III will be estimated with Kaplan-Meier methodology.

CONTACT PERSON FOR THE STUDY

For study related questions please contact:

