1.3.3 Injectafer® Human Experience: Marketed Use and the RLS indicator

The Injectafer® clinical development program demonstrated the effectiveness and safety of Injectafer® in the treatment of IDA. The drug is approved for the treatment of IDA in adult populations who have intolerance to oral iron or have had unsatisfactory responses to oral iron or who have non-dialysis dependent CKD (see Appendix I). Clinical data are currently available from 20 Phase 2 and 3 studies including 5,799 patients, with IDA or IDA associated with CKD who received Injectafer®.

A clinical pharmacokinetic study (VIT-IV-CL-001) using positron emission tomography demonstrated a fast initial elimination of radioactively labeled iron (Fe) ⁵²Fe/⁵⁹Fe Injectafer (ferric carboxymaltose injection) from the blood, with rapid transfer to the bone marrow and rapid deposition in the liver and spleen. Eight hours after administration, 5 to 20% of the injected amount of radioactively-labeled Fe was still detected in the blood.

Important details of pre-clinical and clinical safety and efficacy can be found in the Investigator's Brochure. Ferric carboxymaltose received approval from the United Kingdom (UK) Medicines and Healthcare Products Regulatory Agency (MHRA) on June 15, 2007 (EU Trade name: Ferinject). Injectafer® now has marketing authorization in 63 countries and is currently marketed in 55 of these countries. Injectafer® received approval for the treatment of IDA from the Food and Drug Administration (FDA) on July 25, 2013.

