Non-Responders who do not meet the laboratory criteria for additional dosing will be discontinued from the study and treated for RLS as deemed appropriate by the referring physician. Subjects who are **Non-Responders** at the end of Treatment Phase I and who have met the necessary laboratory criteria (ferritin <300 ng/mL and a TSAT <45%) will consent for enrollment in Treatment Phase II study. These subjects will receive the first of two **unblinded** doses of FCM (undiluted slow IV push 750 mg 100 mg /minute) on Day 0 of Phase II, which will occur within 7 days of completing the Treatment Phase I visit. The subjects will then receive the second dose of FCM (undiluted slow IV push 750 mg 100 mg / minute) on Day 7. All treated subjects will have blood samples taken for hematology, chemistries and iron indices on Day 14. Treatment efficacy (IRLSS), medication review and adverse events assessment by phone will be done on Day 28. All subjects will return to the clinic on Day 42 for end of study assessments. Subjects completing Treatment Phase II will be re-evaluated on Day 42 and defined as either a **Responder** or **Non-Responder**, using the same criteria described above. Those subjects deemed as treatment **Non-Responders** will be discontinued from the study after final assessments are complete.

Subjects who are evaluated on Day 42 (Week 6) as **Responders** from either Treatment Phase I or Treatment Phase II will continue through into the 46-Week, Long-Term Extension Phase III of

the study, and be monitored and assessed by phone for RLS symptoms (IRLSS and HRSQ) and adverse events on Weeks 15, 25, 34, 43 and 52 (final follow-up visit). During Phase III, subjects may receive additional unblinded treatments with FCM if at any time the subject reports worsening of RLS symptoms (an increase >4 points on the IRLSS compared to the last evaluation captured for that subject) and laboratory criteria are met (ferritin <300 ng/mL and a TSAT <45%). Subjects will receive a single FCM 750 mg undiluted slow IV push at 100 mg/minute. See section 6.6 for dosing and assessment outline. No additional treatment will be allowed after the Week 46. A final face-to-face study visit will occur on Week 52. If a clinic visit is not possible, final evaluation will be completed by phone.

	SCREENING	Treatment Phase I and Treatment Phase II				
STUDY VISIT PROCEDURES	-14	DAY 0	DAY 7	DAY 14	DAY 28 (PHONE CONTACT)	DAY 42
Informed Consent	Х					X**
Eligibility	Х	Х				Х

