6.4.1.5 Day 42 (End of Treatment Phase I)

The following should be assessed or obtained:

- Adverse events
- Concomitant medications
- IRLSS will be completed
- Investigator CGI-I Score

- Subject will independently complete the following:
 - ✓ Subject PGI-1 Score
 - ✓ Medical Outcome Study (MOS) Sleep Scale (range 0-100)
 - ✓ Hopkins RLS-Sleep Quality Questionnaire (HRSQ)
- Blood sample for hematology, iron indices, chemistries, and Vitamin D
- Physical exam
- Vital signs (sitting heart rate and blood pressure)
- Brain MRI will be scheduled
- Consent Non-Responders to participate in Treatment Phase II
- Re-educate **Responders** about the 46-week Long-term Extension (Phase III).

Subjects will be assessed by the Investigator and identified as either a treatment **Responder** or a **Non-Responder**. If the subject is a treatment **Non-Responder** in Phase I, the subject will be eligible to re-consent and enroll in Treatment Phase II (section 6.4.2). If the subject is determined to be treatment **Responder**, the subject will continue through into the Long-Term Extension Phase III (section 6.5) of the study.

For **Non-Responder** subjects that do not qualify for treatment Phase II due to laboratory parameters this will be the end of the subject's participation in the study. Subjects should be removed from the study and treated as deemed appropriate by the physician.

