6.4.2 Treatment Phase II (Repeat Days 0 – 42)

The following must be obtained **PRIOR** to scheduling the subject for dosing:

- Confirm consent that the laboratory samples obtained at Day 42 in Treatment Phase I qualifies the Non-Responder for additional treatment with unblinded FCM.
 - \circ Ferritin <300 ng/mL and a TSAT <45%

6.4.2.1 Day 0 and Day 7

Prior to dosing the subject review the following:

- Adverse events
- Concomitant medications
- Vital signs to include temperature.

Once the above procedures have been completed the subject will receive unblinded single FCM at 750 mg (100 mg/minute) undiluted IV push. The following should be verified:

- ✓ Starting and stopping time of FCM administration
- ✓ Total dose in mg and ml of FCM administered (i.e. 750 mg / 15 ml)
- ✓ Blood pressure and heart rate, immediately post and 30 minutes post-study drug administration
- ✓ Adverse events
- ✓ If there are no significant signs or symptoms at the 30 minute post-study drug vital sign assessments, the subject will be released.

6.4.2.2 Day 14

• Blood sample for hematology, chemistries, iron indices, chemistries, and Vitamin D

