2.3 TIME WINDOWS FOR ANALYSIS

No visit window will be constructed. For analyses, only scheduled visits will be summarized in tables.

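### A Phase I non-responder's Day 42 brain MRI can follow the first open-label FCM dose, and the SAP would still report it under the randomised arm

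*Protocol*

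**What the plan says.** **Scan timing.** The protocol synopsis gives the endpoint as "Change from baseline brain MRI-determined iron concentration in the substantia nigra at or within 4 days after Day 42 (Treatment Phase I and II". The schedules (protocol Table 3.2.1, SAP Table 1.1) mark brain MRI in the Day 42 column, and protocol 8.4.2 and SAP 1.2.2 name the endpoint simply as Day 42. For the Phase I Day 42 visit itself, protocol 6.4.1.5 says "Brain MRI will be scheduled".

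**First open-label dose.** Protocol 3.2 has non-responders dosed "on Day 0 of Phase II, which will occur within 7 days of completing the Treatment Phase I visit". The synopsis and SAP 1.3.1 carry the same 7-day limit. None of the three gives a minimum gap.

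**What must precede that dose.** Protocol 6.4.2 asks, before dosing is scheduled, for consent and for Day 42 laboratory samples showing that the result "qualifies the Non-Responder for additional treatment with unblinded FCM" (ferritin below 300 ng/mL and TSAT below 45%). On the dosing day, 6.4.2.1 asks for adverse events, concomitant medications and vital signs. The Phase I MRI is in neither list.

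**Analysis.** SAP 2.3 states: "No visit window will be constructed". SAP 6.2.8, 6.2.9 and 6.3.2 summarise baseline, Day 42 and change in the iron index by randomised group for Phase I. None compares the scan date with a dosing date.

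**The concern.** The Phase I iron-index tables are meant to show FCM against placebo at six weeks. If a placebo non-responder is scanned after a 750 mg open-label dose, that scan is no longer a placebo observation, yet it would enter the placebo mean. Only non-responders who go on to Phase II can be affected, and the plan expects more of them under placebo. The error would therefore not be balanced between the arms.

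The tables concerned cover the substantia nigra, thalamus and motor cortex (secondary), and seven further regions (exploratory, SAP 6.3.2). Protocol 8.5 had planned an analysis of covariance for brain iron at Day 42. After early termination the SAP reports it descriptively, but a mean that mixes exposures is misleading whether or not it is tested.

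**Working it through.** **The plan's own figures.** The plan gives no power or precision for the MRI endpoint. The CGI-I rates borrowed below (50% FCM, 15% placebo, 35 per arm) give 89.6% power by the two-proportion formula, in line with the stated figure of more than 85%.

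**Step 1: the windows (synopsis; protocol 3.2; SAP 1.3.1).**
- Scan: Day 42 to 42 + 4 = Day 46.
- First open-label dose: Day 42 to 42 + 7 = Day 49.
- Overlap: Days 42 to 46.

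**Step 2: allowed day-pairs.** There are 5 scan days and 8 dose days, so 5 × 8 = 40 pairs. The scan falls on a later day than the dose in 4 + 3 + 2 + 1 = 10 pairs, and on the same day in 5. These counts show what the text permits; they are not probabilities.

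**Step 3: laboratory turnaround.** Dosing is scheduled only after the Day 42 ferritin and TSAT are known, so a Day 42 dose is the outer limit of the text. The turnaround time is not given, so it is varied here:

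| Earliest dose day | Allowed pairs | Scan on a later day | Same day |
|---|---|---|---|
| 42 | 40 | 10 | 5 |
| 43 | 35 | 6 | 4 |
| 44 | 30 | 3 | 3 |
| 45 | 25 | 1 | 2 |
| 46 | 20 | 0 | 1 |

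Later-day scans become impossible only if dosing cannot start before Day 46, a turnaround of about 4 days. SAP Table 1.1 also allows the visit at Day 42 + 3. From a Day 45 visit the dose window runs to 45 + 7 = Day 52. The scan limit is then Day 46 if counted from nominal Day 42, or 45 + 4 = Day 49 if counted from the visit.

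**Step 4: who could be affected.** Using lack of CGI-I improvement as a stand-in for non-response:
- Placebo: 35 × (1 − 0.15) = 29.75, about 30.
- FCM: 35 × (1 − 0.50) = 17.5, so 17 to 18 before the laboratory criteria, which should remove more FCM than placebo subjects.

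**Step 5: form of the bias.** Let *s* be the share of Phase II entrants scanned after the dose (same in both arms) and *d* the short-term change in the index caused by that dose. Assume every placebo non-responder enters Phase II.
- If no FCM-arm non-responder fails the laboratory criteria, the shift in the FCM-minus-placebo difference is 0.50*sd* − 0.85*sd* = −0.35*sd*.
- If all of them fail, it is −0.85*sd*.

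Neither *s* nor *d* is in the documents, so this gives the direction for a given sign of *d* but not the size.

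**Step 6: what is not affected.** SAP 2.1 takes the screening scan as the iron-index baseline for both phases. Change in Phase II therefore does not use the Phase I Day 42 scan.

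**The case against.** **The order may be implied.** The 4-day allowance stands in one synopsis bullet, the schedules put the MRI at Day 42, and completing the Phase I visit could be read to include the scan. Scheduling language also appears at screening (protocol 6.2), where the scan must precede dosing because an abnormal baseline MRI is an exclusion. This is a possible reading, but it does not close the gap. An allowance of 4 days after Day 42 contemplates a scan after the visit, as does an instruction to schedule it. Protocol 6.4.2.4, by contrast, simply lists the MRI among the Phase II Day 42 assessments. The screening order follows from an exclusion criterion, and nothing comparable governs Day 42.

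**The effect may be negligible.** This stands in part. No document says how the index behaves within 4 days of a dose. A reader might infer that circulating iron would distort the scan, from the statement in protocol 1.3.3 that "Eight hours after administration, 5 to 20% of the injected amount of radioactively-labeled Fe was still detected in the blood". That section describes fast initial elimination and stops at eight hours, so it does not support such a claim for scans one to four days later.

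**The endpoint carries little weight.** This also stands. It is secondary, and SAP sections 6 and 9 remove formal testing of it.

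**The documents are of different dates.** The supplied protocol was signed in April 2016, while the SAP cites a protocol of 4 September 2019 that was not supplied. The later protocol may already state the order. The absence of a rule in the SAP does not depend on this.

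**Conclusion.** The point holds as a gap in ordering. Under the supplied text, a Phase I non-responder's Day 42 scan can follow open-label FCM by up to 4 days at the outer limit, or by up to 3, 2 or 1 days if laboratory results take 1, 2 or 3 days. The SAP would still tabulate that scan under the randomised arm. More placebo than FCM subjects are exposed to this, so a short-term FCM effect in the same direction as the effect sought would dilute the contrast.

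Three stronger readings are tempting and not supported:
- That a stated percentage of placebo scans is contaminated. The documents give no scan or dosing dates, so any percentage would be an assumed share multiplied by the non-responder rate.
- That about 30 placebo subjects is a firm count. The responder definition also uses the IRLSS score and the subject's request for further treatment; entry to Phase II needs consent; and 35 per arm is the plan for a study that ended early.
- That the three secondary regions are the trial's only brain-iron comparison. SAP 6.3.2 adds seven regions by Phase I group.

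Severity: minor to moderate.

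**What to change.** **SAP 6.2.8, 6.2.9 and 6.3.2.** Compare each Phase I Day 42 scan date with the date of that subject's first Phase II FCM dose. Exclude from the Phase I rows any scan taken after that dose, including a same-day scan not shown to precede it. List the excluded scans with arm and days since dose. This works on data already collected and is still useful after early termination. The cost is one programmed date check and the loss of a few scans from the Phase I table. Because every excluded scan belongs to a non-responder, give the number excluded by arm so that readers can judge the selection.

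**Protocol.** Reconcile the synopsis, 3.2, Table 3.2.1, 6.4.1.5 and 6.4.2 so that they agree on the order of the Phase I Day 42 MRI and the first Phase II dose, after checking the 2019 version. The existing 4-day and 7-day windows can both be met, since Day 46 falls before Day 49, so no visit need be added. This point takes no position on when the dose should be given.
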